4.4.1.2 Hypothesis Testing and Analysis Methods

The following hypotheses will be tested using the Cochran-Mantel-Haenszel (CMH) test³ stratified by genotype (A vs. non-A) and ALT (< 5xULN and ≥ 5xULN) at screening:

H₀: odds ratio of {probability to achieve HBeAg seroconversion in group A} versus {probability to achieve HBeAg seroconversion in group B} = 1

against the alternative

H_a: odds ratio of {probability to achieve HBeAg seroconversion in group A} versus {probability to achieve HBeAg seroconversion in group B} ≠ 1.

The Cochran-Mantel-Haenszel estimates of the common odds ratio, adjusted by stratification factors (genotype (A vs. non-A) and ALT (< 5xULN and ≥ 5xULN)), will be reported, accompanied by the associated 95% confidence intervals. Breslow-Day test will be used to assess the homogeneity of the odds ratios across the strata. The CMH test stratified by genotype (A vs. non-A) and ALT (< 5xULN and ≥ 5xULN) at screening will also be performed based on the PP population.

4.4.1.3 Sensitivity Analysis for Primary Endpoints

In addition to the stratified statistical tests, unstratified tests such as Pearson chi-square test and Fisher's exact test will be performed.

In the primary efficacy analysis, patients with missing values of primary endpoint will be considered as non-responders. In order to evaluate the robustness, sensitivity analysis will be carried out using CMH test, where missing values will be imputed with the approach of last observation carried forward (LOCF).

³ which is a superiority test.

4.4.2 Secondary Efficacy Endpoints

The secondary efficacy analyses will be performed in the ITT population. No hierarchical or sequential testing will be used for secondary efficacy endpoints.

Several secondary parameters will be assessed at the end of treatment/principal observation period, 24 weeks after the end of treatment/principal observation period in primary CSR; in addition, during the extended LTFU period, i.e. at 1, 2, 3, 4 and 5 years after the end of treatment/principal observation period in final CSR.

Secondary efficacy endpoints include two types of endpoints:

- Binary endpoints:
 - HBeAg seroconversion (except HBeAg seroconversion at the time point of 24 weeks at the end of treatment/principal observation period)
 - Loss of HBeAg
 - HBsAg seroconversion
 - Loss of HBsAg
 - Normal ALT (defined as $ALT \leq ULN$, where each ULN is given by each laboratory)
 - Suppression of HBV-DNA:
 - $<20,000$ IU/mL
 - $<2,000$ IU/mL
 - Undetectable (defined as <29 IU/mL as per TAQMAN-HBV QUANT polymerase chain reaction (PCR) assay)
 - Combined endpoints:
 - HBeAg seroconversion and HBV-DNA $<20,000$ IU/ml
 - HBeAg seroconversion and HBV-DNA $<2,000$ IU/mL
- Continuous endpoints:
 - Quantitative serum ALT value, and its change from baseline
 - Quantitative HBV-DNA value, and its change from baseline
 - Quantitative HBeAg value, and its change from baseline
 - Quantitative HBsAg value, and its change from baseline

For all binary endpoints, missing values would be considered as non-responders. For all continuous endpoints, no imputation approach will be implemented to missing values.

Descriptive statistics of the secondary efficacy binary endpoints will be summarized by treatment group. P-values of these binary endpoints will be presented using Fisher's exact test.

Continuous endpoints will be descriptively summarized over time by treatment group. Graphs of continuous secondary endpoints and their corresponding 95% confidence intervals over time will be displayed by treatment group.

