Chronic disease in children is typically characterized by three phases: the immunotolerant phase, the immunoactive phase, and the inactive carrier state. A large majority of pediatric subjects with perinatally acquired HBV infection with HBeAg-positive disease are considered to be immunotolerant. This phase is associated with minimal or no evidence of clinical symptoms, normal ALT levels, and high serum HBV-DNA. This phase can persist throughout childhood, with disease only becoming active with consequent liver damage in a proportion of subjects later in life. Therefore, severe disease with significant fibrosis is very rarely found in children and adolescents, although instances of hepatocellular carcinoma (HCC) and decompensated cirrhosis have been reported [4, 7].

The immunoactive phase normally follows the immunotolerant phase. Early in this phase, there may be high HBV-DNA levels, but then during this phase, the HBV-DNA levels may decrease to < 10,000 copies/mL. It is characterized by varying degrees of liver inflammation and fibrosis and increased levels of aspartate aminotransferase (AST) and ALT. Seroconversion of HBeAg to hepatitis B envelope antibody (HBeAb) occurs leading to the next phase: the inactive carrier state. In the inactive carrier state, patients are HBeAg negative, AST and ALT levels return to normal, and HBV-DNA levels remain very low.

Rates of spontaneous HBeAg seroconversion are much higher in the immunoactive phase than in the immunotolerant phase varying between 8% and 12%. As in adults, a further late phase of reactivated, HBeAg-negative disease can occur. Such patients tend to be older and have more advanced liver disease, however, as this represents a later stage in the natural history of CHB infection.

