2.2 SECONDARY OBJECTIVES

To examine the short and longer term effects on various efficacy and safety measures between a group treated with PEG-IFN monotherapy and an untreated control group, and to evaluate PK in PEG-IFN-treated subjects (see Section 8.1.2), as follows:

Efficacy

- Loss of HBeAg, HBsAg seroconversion (loss of HBsAg and presence of anti-HBs), loss of HBsAg, quantitative serum ALT, proportion of normal ALT, quantitative HBV-DNA, suppression of HBV-DNA < 100,000 copies/mL (< 20,000 IU/mL), < 10,000 copies/mL (< 2,000 IU/mL), undetectable and change from baseline, combined endpoint of HBeAg seroconversion and HBV-DNA < 100,000 copies/mL (< 20,000 IU/mL), and combined endpoint of HBeAg seroconversion and HBV-DNA < 10,000 copies/mL (< 2,000 IU/mL)
- Persistence of HBeAg seroconversion (loss of HBeAg and presence of anti-HBe) over extended long-term follow-up
- Descriptive change from baseline in liver elasticity (in liver elasticity sub-study subjects—see Section 5.3.1.2)

Safety

- AEs (including neurological and psychiatric events), serious and non-serious, and non-serious AEs of special interest
- Laboratory test results (including thyroid function)
- Vital signs (blood pressure, heart rate, temperature)
- Growth: weight and height

Pharmacokinetic

- PK of PEG-IFN following administration of a new BSA-based dosing regimen in PEG-IFN-treated subjects

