8.1.2 Secondary Endpoints

- Loss of HBeAg, HBsAg seroconversion (loss of HBsAg and presence of anti-HBs), loss of HBsAg, quantitative serum ALT, proportion of normal ALT, quantitative HBV-DNA, suppression of HBV-DNA < 100,000 copies/mL (<20,000 IU/mL), < 10,000 copies/mL (<2,000 IU/mL), undetectable and change from baseline, combined endpoint of HBeAg seroconversion and HBV-DNA < 100,000 copies/mL (<20,000 IU/mL), and combined endpoint of HBeAg seroconversion and HBV-DNA <10,000 copies/mL (<2,000 IU/mL) at the end of treatment/principal observation period, 24 weeks after end of treatment/principal observation period, and 1, 2, 3, 4 and 5 years after end of treatment/principal observation period.
- Persistence of HBeAg seroconversion (loss of HBeAg and presence of anti-HBe) at the end of treatment/principal observation period, and 1, 2, 3, 4, and 5 years after end of treatment/principal observation period.
- Descriptive change from baseline in liver elasticity (for subjects enrolled in the liver elasticity sub-study) at the end of treatment/principal observation period, and 24 weeks and 2 years after end of treatment/principal observation period.

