8.2.1.2 Secondary Variables

All secondary variables will be determined at 24 weeks after the end of treatment/principal observation period and at 1, 2, 3, 4, and 5 years after the end of treatment/principal observation period.

- Loss of HBeAg (defined as absence of HBeAg)
- HBsAg seroconversion (defined as loss of HBsAg and presence of anti-HBs)
- Loss of HBsAg (defined as absence of HBsAg)
- Quantitative serum ALT
- Proportion of normal serum ALT (defined as ALT measure \leq ULN)
- Quantitative HBV-DNA
- Suppression of HBV-DNA $< 100,000$ copies/mL ($< 20,000$ IU/mL), $< 10,000$ copies/mL ($< 2,000$ IU/mL), undetectable, and change from baseline
- Combined endpoints: HBeAg seroconversion and HBV-DNA $< 100,000$ copies/mL ($< 20,000$ IU/mL)
- Combined endpoints: HBeAg seroconversion and HBV-DNA $< 10,000$ copies/mL ($< 2,000$ IU/mL)
- HBeAg seroconversion (defined as absence of HBeAg and presence of HBeAb)

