4.4.1 Primary Efficacy Endpoint

4.4.1.1 Definition of Primary Efficacy Endpoint

The primary efficacy endpoint is HBeAg seroconversion at 24 weeks after the end of treatment/ principal observation period for Group A and Group B. HBeAg seroconversion

is defined as absence of HBeAg (that is, a negative result for HBeAg) and presence of anti-HBe (that is, a positive result for anti-HBe).

The response rate of HBeAg seroconversion for a particular analysis population will be determined by:

$$\frac{\text{The number of patients with Negative HBeAg and Positive HBeAb at each visit}}{\text{The number of patients in each group for that analysis population}} \times 100\%.$$

Patients without either HBeAg or anti-HBe at 24 weeks after the end of treatment/principal observation period will be counted as non-responders. Patients in Group B who switched to receive PEG-IFN after Week 48 and prior to 24 weeks post-observation period will also be counted as non-responders.

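### Persistence of HBeAg seroconversion is a named secondary endpoint, but the planned analysis is a visit-by-visit ITT rate that cannot show whether responses last

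*SAP*

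**What the plan says.** The objective in protocol 2.2 is "Persistence of HBeAg seroconversion (loss of HBeAg and presence of anti-HBe) over extended long-term follow-up". Protocol 8.1.2 repeats it as an endpoint, "Persistence of HBeAg seroconversion (loss of HBeAg and presence of anti-HBe) at the end of treatment/principal observation period" and at Years 1 to 5. The synopsis reproduced in SAP Appendix 1 keeps the same wording.

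The analysis definitions drop the idea of persistence. Protocol 8.2.1.2 lists only "HBeAg seroconversion (defined as absence of HBeAg and presence of HBeAb"), that is, status at a visit. SAP 4.4.2 lists "HBeAg seroconversion (except HBeAg seroconversion at the time point of 24 weeks at the end of treatment/principal observation period") among the binary endpoints and adds: "The secondary efficacy analyses will be performed in the ITT population". It also says: "For all binary endpoints, missing values would be considered as non-responders". P-values come from Fisher's exact test.

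The only rate formula, in SAP 4.4.1.1, has as numerator "The number of patients with Negative HBeAg and Positive HBeAb at each visit" and as denominator everyone in the group for that population. The subgroup and logistic analyses (SAP 4.4.3 and 4.4.4) concern follow-up Week 24 only. SAP 2.4 says only that long-term data will be summarised in the final report.

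**The concern.** Persistence asks what becomes of children who have responded. A rate over the whole group at Year 3 or Year 5 does not ask that. It counts a child who kept the response and a child who converted for the first time in the same way. It also counts a relapse and a missed visit in the same way.

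The documents give three routes by which new responses can enter the long-term rates:

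- **Spontaneous conversion.** Protocol 1.1.1 states: "Rates of spontaneous HBeAg seroconversion are much higher in the immunoactive phase than in the immunotolerant phase varying between 8% and 12" per cent. Protocol 1.2 suggests, with hedging, that untreated children may reach similar overall rates with a lag of 2 to 3 years, which lies inside the 5-year follow-up.
- **Other anti-HBV therapy.** Protocol 4.4 generally prohibits it only up to follow-up Week 24.
- **Late switching in Group B.** The switch offer stays open for a year after Week 48. The rule that counts switchers as non-responders (protocol 8.2.4.1, SAP 4.4.1.1) covers only switches before the visit 24 weeks after the observation period.

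At stake is how the final report is read. A table labelled persistence would be taken as durability of response, and it would not measure that.

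**Working it through.** The documents state no figure for persistence, so there is none to reproduce. The nearest planned number is the sample size (SAP 2.3, protocol 8.2.2): 145 children, 2:1, 32% against 10%. The continuity-corrected formula gives 96 + 48 = 144. Without the correction it gives 126, and 145 then has 86.6% power. That calculation is not in dispute; it supplies the group sizes below.

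**Inputs**

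- Group sizes: 145 × 2/3 = 96.7 and 145/3 = 48.3, taken as 97 and 48.
- Responders at follow-up Week 24: 0.32 × 97 = 31.0 and 0.10 × 48 = 4.8, so about 31 and 5.
- Conversion rate s: 8% to 12% (protocol 1.1.1). No time unit is given and the figure describes spontaneous conversion. Reading it as per year, and applying it to PEG-IFN non-responders, are assumptions.
- Relapse rate r: not in the documents; assumed 0% to 20% per year.
- Time: follow-up Week 24 is taken as 0.5 year after treatment, so Year 1 is t = 0.5 and Year 5 is t = 4.5.
- No missing data in step 1.

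**Step 1: planned rate against durability.** Use a two-state model in which children convert and relapse at constant rates:

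- a = −ln(1 − s), b = −ln(1 − r), π = a/(a + b)
- planned ITT rate: P(t) = π + (0.32 − π) × exp[−(a + b)t]
- uninterrupted response among Week 24 responders: D(t) = (1 − r)^t

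For s = 10% and r = 20%: a = 0.1054, b = 0.2231, π = 0.3207.

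- Year 1: P = 32.0%; D = 0.8^0.5 = 89%.
- Year 5: P = 0.3207 − 0.0007 × 0.228 = 32.1%; D = 0.8^4.5 = 37%, or about 11 of 31 children.

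Other Group A scenarios at Year 5:

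| s per year | r per year | Planned ITT rate | Uninterrupted response |
|---|---|---|---|
| 0 | 0 | 32.0% | 100% |
| 10% | 20% | 32.1% | 37% |
| 8% | 20% | 28.4% | 37% |
| 8% | 10% | 39.0% | 62% |
| 12% | 5% | 53.8% | 79% |
| 8% | 0 | 53.3% | 100% |

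The first two rows give the same planned result with durability of 100% and 37%. The fourth row shows the rate rising above 32% while durability falls.

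**Step 2: missing results.** With no relapse and no conversion, 20% missing turns 32% into 0.32 × 0.8 = 25.6%. Attrition alone then looks like loss of response.

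**Step 3: what a responder-based figure could show.** If 25 of 31 Group A responders kept their response, the estimate is 81% with an exact 95% CI of 63% to 93%. In Group B, 4 of 5 gives roughly 28% to 99%.

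**The case against.** The best defence is that the SAP follows the protocol. Protocol 8.1.2 counts the end of treatment as a persistence time point and 8.2.1.2 defines visit status, so the word may have been meant loosely as the rate over time. The visit-level ITT rate is also the right randomised comparison for the case in protocol 1.2, which is about earlier seroconversion. Both points stand. They are reasons to keep that rate, but they leave the stated objective unanswered and the label misleading.

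Three further objections have weight:

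- Restricting to responders conditions on a post-randomisation outcome, and about 5 children in Group B will support almost no inference. The added table must be descriptive.
- No passage says which response is to persist. Follow-up Week 24 is a choice, made here because it is the primary endpoint; an end-of-treatment anchor is also possible.
- Table layouts are in DAP Module 2, which is not part of the protocol or SAP and might hold a responder table. The SAP describes that module as layout, however, and the SAP is where methods are set.

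A reader might infer that protocol 1.2 justifies interferon by lasting response. It does not: the advantages it gives over nucleos(t)ides are a defined treatment duration and absence of resistance.

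**Conclusion.** The point holds as a gap in definition and analysis. Persistence is promised, only visit status is analysed, and the planned rates cannot identify durability. That conclusion follows from the numerator, the denominator and the missing-data rule, and does not depend on any assumed rate.

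The size can only be illustrated. With 10% conversion and 20% relapse per year, a flat rate near 32% hides a fall in uninterrupted response from 89% to 37%. Both rates are assumptions.

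Two stronger readings are tempting and unsupported. One is that the planned figure must overstate persistence or stay above 32%; the 28.4% and 25.6% cases contradict that. The other is that late spontaneous converters will in fact replace relapsers. The documents give no relapse rate and no time unit for the 8% to 12%, so the direction of any distortion is unknown.

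The primary endpoint is unaffected. The change should be made before the long-term data are analysed.

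**What to change.** In SAP 4.4.2:

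1. Keep the ITT seroconversion rate at each visit as the randomised comparison.
2. Add a descriptive persistence analysis. Among children who met the primary endpoint at follow-up Week 24, give the proportion still HBeAg-negative and anti-HBe-positive at Years 1, 2, 3, 4 and 5, by group, with exact 95% CIs. Show relapse, missing result and start of other anti-HBV therapy as separate categories. State how a response lost and then regained is counted.
3. Report new seroconversions among Week 24 non-responders separately, split by whether they followed other anti-HBV therapy or a PEG-IFN switch.
4. Label the end-of-treatment figure as response at that time point, not persistence.

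Align protocol 8.1.2, 8.2.1.2 and the synopsis at the next amendment.

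Cost: SAP text, a small number of tables and a minor protocol wording change, which goes through the review in protocol Section 13. No new samples are needed, because HBeAg and anti-HBe are already scheduled at Years 1 to 5. The limits are small denominators (about 31 and 5) and no randomised comparison for the responder-only table.

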3.1 OVERVIEW OF STUDY DESIGN AND DOSING REGIMEN

This is a 2:1 randomized, controlled, parallel-group, open-label, multicenter study of PEG-IFN treatment compared to an untreated control ([Figure 1](#)). Subjects without advanced fibrosis/cirrhosis will be randomized 2:1 to PEG-IFN treatment (Group A) or untreated control (Group B), respectively. Subjects with advanced fibrosis will be assigned to PEG-IFN treatment (Group C). Subjects in Groups A and C will receive PEG-IFN for 48 weeks. The first 48 weeks from randomization will be referred to as the treatment period for Groups A and C and the principal observation period for Group B. The primary endpoint will be assessed 24 weeks after the end of treatment/principal observation period.

Forty-eight weeks after randomization, PEG-IFN will be offered to subjects in the Group B untreated control group who have not experienced HBsAg seroconversion. This offer will be available for up to 1 year following Week 48. If eligible, these subjects will enter the switch arm, where they will receive PEG-IFN for 48 weeks.

The screening period will be up to 35 days. For Group A, Group B non-switch, and Group C subjects the study length is approximately 6 years (1-year treatment/principal observation period and 5 years of follow-up). For Group B switch subjects the study length is up to approximately 8 years (1-year principal observation period, up to 1 year follow-up whilst deciding whether to switch, 1-year switch treatment period, and 5-year follow-up period).

Figure 1 Schematic of Study Design

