4.8 SWITCH CRITERIA

Forty-eight weeks after randomization, PEG-IFN will be offered to subjects in the Group B untreated control group who have not experienced HBeAg seroconversion. This offer will be available for up to 1 year following Week 48. Subjects must meet the following switch inclusion and exclusion criteria.

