4.8.1 Switch Inclusion Criteria

Subjects in Group B may switch to treatment with PEG-IFN if the answer to all of the following statements is "yes."

- Positive HBeAg and positive HBsAg within 6 months prior to switch baseline
- Either
 - A liver biopsy performed within 2 years prior to switch baseline to exclude cirrhosis (see [Appendix 1](#)) or
 - Clinical, laboratory, and ultrasound data which together exclude cirrhosis

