4.6.5.2 Summary of Growth Measurements

All growth variables will be listed by treatment group and center/patient number in Safety Population, including raw height (weight, BMI) measurements at each visit, height (weight, BMI) for age z-scores and height (weight, BMI) for age percentiles (actual value and change from baseline).

Descriptive summaries of the z-scores and percentiles for height, weight and BMI for age (actual value and change from baseline) for patients in Safety Population will be presented by visit.

Patients with height (weight, BMI) for age percentile drop ($\geq 15\%$) from baseline will be summarized and listed by treatment group in Safety Population.

Plots of the mean (and 95% CI) of z-score and percentile for height, weight and BMI for age by treatment group in Safety Population will be depicted from the study baseline to 24 weeks after the end of treatment/principal observation period.

Plots of the mean change from the baseline (and 95% CI) of z-score and percentile for height, weight and BMI for age by treatment group in Safety Population will be depicted from the study baseline to 24 weeks after the end of treatment/principal observation period.

Individual change from baseline plots of z-score and percentile for height, weight and BMI for age by group will be depicted.

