4.8 ANALYSES OF SWITCH ARM

By the clinical cutoff for the primary CSR (24 weeks after the end of treatment period (Group A) or principal observation period (Group B)), very few patients in Switch arm would have completed their 24 week follow-up period after completion of treatment. Hence, only listings of deaths, SAEs, and AEs leading to discontinuation of study treatment will be presented in the primary CSR. All the other efficacy and safety data for Switch arm will be summarized and reported in the final CSR.

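### Continuous efficacy means for Group B at follow-up Week 24 would rest on observed cases after HBeAg-positive children have begun leaving for the Switch arm, and the SAP sets no rule for this

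*SAP*

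**What the plan says.** SAP 4.4.2 names four continuous secondary efficacy endpoints: ALT, HBV-DNA, quantitative HBeAg and quantitative HBsAg, each as a value and as a change from baseline. On analysis it says "Continuous endpoints will be descriptively summarized over time by treatment group", with graphs and 95% confidence intervals. On missing data it says "For all continuous endpoints, no imputation approach will be implemented to missing values". For the binary endpoints of the same section the rule differs: "For all binary endpoints, missing values would be considered as non-responders".

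Protocol 4.8 sets who may leave the control group: "PEG-IFN will be offered to subjects in the Group B untreated control group who have not experienced HBeAg seroconversion". Entry under 4.8.1 also requires "Positive HBeAg and positive HBsAg within 6 months prior to switch baseline". Protocol 5.3 and footnote a of Protocol Table 3 open this window at Week 48 and close it one year later. A child who switches then follows the Switch schedule. SAP 2.4 and 4.8 put only disposition and a few listings for these children in the primary CSR; SAP 4.8 then says "All the other efficacy and safety data for Switch arm will be summarized and reported in the final CSR".

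The SAP says how to treat a child who switches before follow-up Week 24 in one place only. That is 4.4.1.1, where such a child is a non-responder for the primary endpoint.

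For growth, SAP 4.6.5.2 plots means that "will be depicted from the study baseline to 24 weeks after the end of treatment/principal observation period" and gives no missing-data rule.

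Protocol 3.1 words the switch offer differently, as open to Group B children "who have not experienced HBsAg seroconversion".

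**The concern.** Departure from Group B depends on the outcome under study. Children who have seroconverted are not offered the switch. Children who have not may leave at any time from Week 48, and their later values then belong to another arm's report. With neither imputation nor a longitudinal model for the continuous efficacy endpoints, the late Group B mean is an average over whoever is left, and seroconverters make up a growing share of them. The confidence interval around that mean reflects the smaller number but not the selection.

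Two summaries of the same marker at the same visit would also use different sets of children. The proportion with HBV-DNA below 2,000 IU/mL is taken over all of Group B, with switchers counted as failures. Mean HBV-DNA is taken over the remnant. The first can make the control arm look worse than an untreated arm would; the second can make it look better. Follow-up Week 24 is the off-treatment visit at which the primary endpoint is read, so readers will look at these means beside it.

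**Working it through.** **1. Which endpoints are exposed, and when** (Group B schedule, Protocol Table 3)

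| Visit | HBV-DNA | ALT (chemistry) | Quantitative HBeAg/HBsAg | Exposed to switching |
|---|---|---|---|---|
| Week 48 | scheduled | scheduled | scheduled | none |
| Follow-up Week 12 | scheduled | not scheduled | not scheduled | HBV-DNA only |
| Follow-up Week 24 | scheduled | scheduled | scheduled | all four |
| Years 1, 2, 3, 4, 5 | scheduled | not scheduled | not scheduled | HBV-DNA only |

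Week 48 is clean because Protocol 5.3 places the switch baseline at the final pre-switch visit. For the same reason, a child who switches at the follow-up Week 24 visit still contributes that visit. By Year 1 the window is closing, so the selection is then close to complete.

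**2. Size of Group B.** The inputs are in SAP 2.3: 32% against 10%, two-sided 0.05, at least 80% power. Allocation is 2:1.

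- Pooled rate: (0.10 + 2 x 0.32)/3 = 0.2467.
- Control n without continuity correction: [1.960 x sqrt(1.5 x 0.2467 x 0.7533) + 0.842 x sqrt(0.10 x 0.90 + 0.32 x 0.68/2)]^2 / 0.22^2 = 41.1. This rounds up to 42, or 126 in total.
- With continuity correction: (41.1/4) x [1 + sqrt(1 + 6/(2 x 41.1 x 0.22))]^2 = 47.7. This rounds up to 48, or 144 in total.

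The stated total is 145, so the corrected calculation reproduces it to within one child. Group B is therefore about 48 (145/3 = 48.3).

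**3. Seroconverter share of the remnant.** Take 10% of 48, about 5 children, as seroconverted, which leaves 43. Let s be the share of those 43 who have switched before the follow-up Week 24 visit. The documents do not give s, so it is an assumption.

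Share = 5 / (5 + 43(1 - s)), against 5/48 = 0.104 in the full arm.

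**4. Shift in mean HBV-DNA.** Let D be the gap between seroconverters and others, assumed to be 2 to 4 log10. Shift = (share - 5/48) x D.

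| s | Retained n | Share | Rise | Shift, D = 2 | Shift, D = 4 |
|---|---|---|---|---|---|
| 25% | 37.25 | 0.134 | 0.030 | 0.06 | 0.12 |
| 50% | 26.5 | 0.189 | 0.085 | 0.17 | 0.34 |
| 75% | 15.75 | 0.317 | 0.213 | 0.43 | 0.85 |

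**5. Sensitivity.** Using exactly 10% in place of 5/48 gives shares of 12.9%, 18.2% and 30.8%. Over the 8% to 12% spontaneous range in Protocol 1.1.1, the share is 14.8% to 21.4% at s = 50% and 25.8% to 35.3% at s = 75%. At s = 76% the remnant reaches the 32% assumed for Group A.

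The calculation holds the number of seroconverters fixed after Week 48 and treats switching as random among the rest.

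**The case against.** The strongest reply is that the SAP never says post-switch values are dropped. SAP 4.1.1 assigns children as randomised, and if their later values were kept in Group B there would be no selection. That is correct: exclusion is implied by the separate schedule and the deferral to the final CSR, not stated. But keeping the values would put treated children into the untreated mean. Either way a rule is missing.

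Second, these outputs are descriptive. Protocol 8.2.5 plans no formal test for quantitative ALT or HBV-DNA, and the SAP plans no A-B difference for any of the four. The end of the observation period is already a reported time point, and SAP 4.2 counts children completing 12 and 24 weeks of follow-up. This stands and limits the importance of the point.

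Third, the remnant is not simply seroconverters plus families who declined. It also holds children who have not yet switched and children barred under Protocol 4.8.2, and seroconverters may themselves withdraw. This stands too, and makes the effective s uncertain. One of those bars is ALT above 10 x ULN, which keeps some non-seroconverters with high ALT in Group B and pulls its ALT mean upward.

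Three stronger readings are tempting but unsupported:

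- A reader might infer that all four markers are affected at follow-up Week 12. Table 3 schedules only HBV-DNA among them at that visit.
- A reader might infer that the growth curves carry the same bias. The no-imputation sentence belongs to the efficacy section. Protocol 8.2.5.3 and the synopsis in SAP Appendix 1 name REML or analysis of covariance for growth, and the documents give no link between seroconversion and growth from which to derive a direction.
- A reader might infer that the primary result is in doubt. It has its own switcher rule in SAP 4.4.1.1.

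**Conclusion.** The point holds for the continuous secondary efficacy endpoints: all four at follow-up Week 24, and HBV-DNA alone at follow-up Week 12 and at Years 1 to 5. Read as written, the plan yields Group B means and intervals from a group selected on HBeAg status.

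For HBV-DNA the selection makes the control arm look better and so understates PEG-IFN, provided switching among non-seroconverters is unrelated to viral load. The direction for ALT is less certain. The size depends on two figures that the documents do not give, the switch rate and the log10 gap. It is small at 25% switching and could approach 0.85 log10 at 75%.

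The primary test and the Week 48 summaries are untouched. This is a low-cost improvement to descriptive secondary results.

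**What to change.** In SAP 4.4.2:

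- State that values after the switch date are excluded from the Group B continuous summaries.
- Show, at each visit, the number contributing and the number switched, and present Week 48 beside follow-up Week 24.
- Add a prespecified estimate of the group means and the A-B difference at follow-up Week 24, from multiple imputation or a mixed model. It should use all pre-switch visits, the baseline value and the stratification factors.
- Use Week 48 HBeAg status only as an auxiliary variable for imputation. It must not be a covariate in the treatment contrast: it is measured after randomisation and may be affected by treatment, so adjusting for it can remove part of the effect.

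In SAP 4.6.5, carry forward the REML or analysis-of-covariance method that the protocol and SAP Appendix 1 already name, applied to pre-switch data, and state a missing-data rule.

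Protocol 3.1 (HBsAg) and 4.8 (HBeAg) must be reconciled on who is offered the switch. The working above follows 4.8. The selection would remain under either wording while 4.8.1 requires positive HBeAg.

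The cost is SAP text and modest programming, with no new data. The added estimate rests on a missing-at-random assumption given recorded HBeAg status. That is easier to defend than observed-case means, but it cannot be verified.
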